10.8 STUDY CALENDAR

Trial Period:	Screening Phase	Treatment Cycles								End of Treatment	Post-Treatment	
Treatment Cycle/Title:	Screening	1	2	3	4	To be repeated every 4 weeks until progression or toxicity up to 24 months				EOT (at time of discontinuation)	Safety Follow-up	Survival Follow-Up ¹
Scheduling Window (Days):	(-28 to -1 days)		± 3	± 3	± 3	± 3	± 3	± 3	± 3	± 3	30 days (+ or – 7 days) post discontinuation	Every 12 weeks (+ or – 7 days)
Administrative Procedures												
Informed Consent	X											
Inclusion/Exclusion Criteria	X											
Demographics and Medical History	X											
Prior and Concomitant Medication Review	X											
Post-study anticancer therapy status											X	X
Survival Status												X
Clinical Procedures/Assessments												
Review Adverse Events		X	X	X	X	X	X	X	X	X	X	
Review Concomitant Medication		X	X	X	X	X	X	X	X	X	X	
Physical Examination	X	X	X	X	X	X	X	X	X	X	X	
Vital Signs (temperature/pulse/respiratory rate/blood pressure and weight)	X	X	X	X	X	X	X	X	X	X	X	
ECOG Performance Status	X	X	X	X	X	X	X	X	X	X	X	
12-Lead ECG	X											
Echocardiogram	X											
Administration of nivolumab plus relatlimab over 60 minutes IV		X	X	X	X	X	X	X	X	X		
Laboratory Procedures/Assessments: analysis performed by LOCAL laboratory												
Pregnancy Test – Urine or Serum β-HCG ²	X	X	X	X	X	X	X	X	X	X	X	
CBC with Differential	X	X	X	X	X	X	X	X	X	X	X	

Trial Period:	Screening Phase	Treatment Cycles								End of Treatment	Post-Treatment		
		1	2	3	4	To be repeated every 4 weeks until progression or toxicity up to 24 months					EOT (at time of discontinuation)	Safety Follow-up	Survival Follow-Up ¹
Treatment Cycle/Title:	Screening					5	6	7	8				
Scheduling Window (Days):	(-28 to -1 days)		± 3	± 3	± 3	± 3	± 3	± 3	± 3	± 3	± 3	30 days (+ or - 7 days) post discontinuation	Every 12 weeks (+ or - 7 days)
Comprehensive Serum Chemistry Panel	X	X	X	X	X	X	X	X	X	X	X	X	
LDH	X	X	X	X	X	X	X	X	X	X	X	X	
T3, freeT4 and TSH ³	X		X		X		X		X		X	X	
ACTH and serum cortisol ³	X		X		X		X		X		X	X	
Amylase ³	X	X	X	X	X	X	X	X	X	X	X	X	
Lipase ³	X	X	X	X	X	X	X	X	X	X	X	X	
Urinalysis	X	X	X	X	X	X	X	X	X	X	X	X	
HBsAg, HBsAb, Hep C Ab, HB core antibody ⁴	X												
Troponin T ^{3,5}	X	X	X										
PT/INR and PTT	X												
Efficacy Measurements													
CT chest plain	X			X		X		X					
MRI Brain with and without contrast ⁶	X												
MRI abdomen/ pelvis with EOVIST™ with and without contrast ⁷	X			X		X		X					
Archival Tissue Collection/Correlative Studies Blood													
Correlative Studies Blood Collection ⁸	X	X	X	X						X ⁸			
One additional blood sample for correlative studies			X ⁹										
Archival Tumor Tissue Collection ¹⁰	X												
Fresh Tumor Biopsies ¹¹	X									X ¹¹			

1. For two years.
2. For women who are able to become pregnant only.
3. Also as needed according to clinical signs and symptoms
4. For patients with treated hepatitis C, undetectable viral load is required with positive antibodies
5. For the first two months then as dictated by clinical signs and symptoms thereafter
6. At baseline, every 6 months and as needed as dictated by clinical signs and symptoms.
7. EOVISt contrast preferred but not mandatory
8. Blood for correlative studies to be obtained on day 1 of cycles 1-3 prior to treatment and upon progression/response
9. One additional blood sample for correlative studies will also be collected at any point after treatment started and before progression of disease or end of treatment
10. If fresh biopsy determined to be not safe and archival tissue available, then fresh biopsy waived.
11. Fresh tumor biopsies will be obtained at screening and upon progression or response if needed, safe and feasible as determined by the investigator.

11 CORRELATIVE STUDIES

Research Sampling	Time point	Contents
Archival Tissue	Screening	FFPE Tumor Tissue
FFPE Biopsy Tissue	Pre-treatment Biopsy	FFPE Biopsy Tissue
	Treatment Response or Progression	
Fresh Tissue, Fresh-Frozen Tissue	Pre-treatment Biopsy	Fresh Tumor Tissue, Fresh-Frozen Tumor Biopsy Tissue
	Treatment Response or Progression	
Blood	Pre-treatment C1	4- 10mL EDTA purple top tube
	Pre-Treatment C2	
	Pre-Treatment C3	
	One additional blood sample for correlative studies will also be collected at any point after treatment started and before progression of disease or end of treatment	
	At time of Response or Progression	

Correlative studies will be conducted for research use only.

For participants who consent to additional correlative studies, archival tissue, blood, and fresh/fresh-frozen tumor from pre- and post- treatment biopsy will be collected for correlative biomarker analysis including but not limited to tumor single-cell RNA-sequencing with single-cell TCR/BCR profiling, metastatic tumor mutation profiling, blood-based bulk TCR profiling, and blood-based cell-free DNA mutation profiling.

Correlative Studies, Solid Tumors:

Archival FFPE primary or previous metastatic tumor specimen, if available, may be collected from previous/current surgeries or biopsies for biomarker analysis including but not limited to mutation analysis and immunohistochemistry of LAG-3 and PD-1. A minimum of 3 10-micron sections will be required. Fresh/fresh-frozen tumor tissue from pre- and post- treatment biopsies will be collected for biomarker analysis including but not limited to tumor single-cell RNA-sequencing with single-cell TCR/BCR profiling. Mutation analysis may be conducted on fresh-frozen tumor tissue from pre- and post- treatment biopsy, if quantity permits.

Correlative Studies, Blood:

Blood will be obtained using EDTA purple top tubes and will be stored as plasma and buffy coat at -80 °C. Blood sample analysis will consist of but is not limited to bulk TCR profiling and cell-free DNA profiling.

Sample Storage and Analysis

Storage and analysis for tumor and blood will be conducted at:

The laboratory of [name]
Department of Ophthalmology
[name]
Biomedical Research Building
[name]

12 EVALUATION CRITERIA

12.1 Parameters of Outcome –RECIST 1.1 Criteria

12.2 Definition of Measurable Lesions

Measurable disease is defined as at least one lesion that can be accurately measured in at least one dimension (longest dimension to be recorded). Each lesion must be ≥ 20 mm when measured by conventional techniques, including palpation, plain x-ray, CT, and MRI, or ≥ 10 mm when measured by spiral CT.

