2 OBJECTIVES AND ENDPOINTS

Objectives	Endpoints
Primary	
To evaluate efficacy of the combination of nivolumab and BMS-986016 in terms of objective response rate (ORR) according to RECIST v1.1.	Primary endpoint for this study will be best objective response rate (ORR).
Secondary	
To evaluate the disease control rate (DCR), progression-free survival (PFS), overall survival (OS), duration of response (DOR) and safety profile of the combination of nivolumab and BMS-986016	Secondary endpoints will include disease control rate (DCR), progression-free survival (PFS), overall survival (OS), median duration of response (mDOR) and safety profile (AEs, SAEs).
Exploratory	
Tumor microenvironment (TME) in fresh biopsies pre- and post-treatment and at progression	Evaluate pre-treatment characteristics of the TME that may predict for response or lack of response. Learn the effects of treatment on the TME.
Blood samples at baseline and predetermined post-treatment time points and at progression	T cell receptor profiling Circulating tumor cell DNA.

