4 STUDY POPULATION

4.0 Inclusion Criteria

Patients participating in this study must:

1. Have a biopsy-proven diagnosis of metastatic uveal melanoma, previously untreated with anti-PD-1,CTLA-4 and/or LAG-3 blocking antibodies.
2. Agree to undergo a pre-treatment and a post-treatment fresh biopsy of the tumor, if needed, safe and feasible as determined by the investigator.
3. Have completed all previous therapy for a minimum of 3 weeks before the first dose of experimental treatment. All adverse events of previous therapy must have resolved. Palliative radiation therapy to a limited field is allowed within this 3 week period.
4. Be willing and able to provide written informed consent/assent for the trial.
5. Be ≥ 18 years of age on day of signing informed consent.
6. Have measurable disease based on RECIST 1.1.
7. Have a performance status of 0-2 on the ECOG Performance Scale.
8. LVEF assessment with documented LVEF $\geq 50\%$ by either TTE or MUGA (TTE preferred test) within 6 months from first study drug administration
9. Demonstrate adequate organ function as defined in **Error! Reference source not found..** All screening labs should be performed within 10 days of treatment initiation.

Table 1. Adequate Organ Function Laboratory Values

System	Laboratory Value
Hematological	
Absolute neutrophil count (ANC)	$\geq 1,500$ /mcL
Platelets	$\geq 100,000$ / mcL
Hemoglobin	≥ 9 g/dL or ≥ 5.6 mmol/L (within 7 days of assessment)
Renal	
Serum creatinine OR Measured or calculated ^a creatinine clearance (GFR can also be used in place of creatinine or CrCl)	≤ 1.5 X upper limit of normal (ULN) OR ≥ 30 mL/min for subject with creatinine levels > 1.5 X institutional ULN
Hepatic	
Serum total bilirubin	≤ 1.5 X ULN OR Direct bilirubin \leq ULN for subjects with total bilirubin levels > 1.5 ULN
AST (SGOT) and ALT (SGPT)	≤ 2.5 X ULN OR ≤ 5 X ULN for subjects with liver metastases
Albumin	> 2.5 mg/dL
Coagulation	
International Normalized Ratio (INR) or Prothrombin Time (PT)	≤ 1.5 X ULN unless subject is receiving anticoagulant therapy as long as PT or PTT is within therapeutic range of intended use of anticoagulants
Activated Partial Thromboplastin Time (aPTT)	≤ 1.5 X ULN unless subject is receiving anticoagulant therapy

	as long as PT or PTT is within therapeutic range of intended use of anticoagulants
^a Creatinine clearance should be calculated per institutional standard.	

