10.2 Cycle 1, 3, 5, 7, Day 1 + or – 3 days

The following assessments will be performed

- Review adverse events
- Review concomitant medication

- Physical Exam
- Vital Signs: systolic and diastolic blood pressures, and temperature
- ECOG Performance Status
- Administration of nivolumab plus relatlimab
- Laboratory Evaluations
 - Pregnancy Test (Urine or Serum β -HCG²)
 - CBC with differential
 - Comprehensive metabolic panel
 - LDH
 - Amylase
 - Lipase
 - Urinalysis
 - Troponin T (Only cycle 1)
- CT chest plain (Only for cycles 3,5,7, Day 1 (+ or – 3 days))
- MRI abdomen and pelvis with and without contrast (EOVIST® preferred) (Only for cycles 3,5,7, Day 1 (+ or – 3 days))
- Correlative studies
 - Blood for correlative studies to be obtained on
 - Cycle 1, Day 1 (+ or – 3 days)
 - Cycle 3, Day 1 (+ or – 3 days)
 - upon progression or response
 - Fresh tumor biopsy if needed, safe and feasible as determined by investigator.

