12.4 Baseline documentation of “Target” and “Non-Target” lesions

All measurable lesions up to a maximum of 5 lesions per organ and 10 lesions in total representative of all involved organs should be identified as target lesions and will be recorded and measured at baseline. Target lesions should be selected on the basis of their size (lesions with the longest dimension) and their suitability for accurate repetitive measurements by one consistent method of assessment (either by imaging techniques or clinically). A sum of the longest dimension (LD) for all target lesions will be calculated and reported as the baseline sum LD. The baseline sum LD will be used as reference to further characterize the progression of the measurable dimension of the disease. Tumor within a previously irradiated field will be designated as “non-target” lesions unless progression is documented or a biopsy is obtained to confirm persistence at least 90 days following completion of radiation therapy.

All other lesions (or sites of disease) should be identified as non-target lesions and should also be recorded at baseline. Measurements are not required and each of these lesions should be followed as stable (the persistence of a non-target lesion), complete response (the disappearance of a non-target lesion) or progressive disease (the unequivocal progression of a non-target lesion).

All baseline evaluations of disease status should be performed as close as possible to the start of treatment and never more than 4 weeks before the beginning of treatment.

Measurement of the longest dimension of each target lesion size is required for follow-up. Change in the sum of these dimensions affords some estimate of change

in tumor size and hence therapeutic efficacy. All disease must be assessed using the same technique as baseline.

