12.6 Progression for Patients with Non-Measurable Disease at Baseline

Defined as increasing clinical, radiological, or histological evidence of disease since study entry. Survival is the observed length of life from the date of study entry to death or the date of last contact.

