16.3 Statistical Analyses

Demographic and disease characteristics will be summarized using descriptive statistics. Counts and percentages will be used to summarize the distribution of categorical variables. Median, range, mean, and standard deviation will be used for continuous variables. Continuous variables will be tested using Student's t-test and/or Mann-Whitney U test. All statistical tests will be two-sided and $p < 0.05$ will be considered as statistical significance.

The full analysis set will consist of all patients enrolled. The modified full analysis set will consist of all enrolled patients, except patients withdrawn prior to the first efficacy measurement (at Cycle 2). The per-protocol analysis set will consist of all patients from the FU analysis set without any major protocol violations. The safety analysis set will consist of all patients who get treatment regardless of completion of treatment. The safety analysis set will serve as the main analysis set for safety assessments. The modified full analysis set will serve as the main analysis set for efficacy assessments. The efficacy assessment will also be performed on the per-protocol and full analysis sets.

Response rate will be estimated along with corresponding 95% confidence interval using Fisher's exact method. Tumor response (CR, PR, SD, or PD) will be defined according to RECIST v1.1 guideline. Objective response rate (ORR) will be the proportion of patients with a confirmed CR or PR and disease control rate (DCR) is calculated by the proportion of patients with confirmed CR, PR, or SD.

Progression-free survival (PFS) is defined as the time from the date of enrollment to the date that objective progression disease is documented or death due to any cause, whichever occurs first. Overall survival (OS) is defined as the time from the date of enrollment to the date of death. Duration of response is defined as the time from the date of first documented response (CR or PR) until date of documented progression or death in the absence of disease progression.

For PFS and OS, Kaplan-Meier method will be used to estimate survival rates for pre-specified time points along with 95% confidence intervals.

Safety analysis will be include detailed tabulations of adverse events by type, grade and treatment attribution.

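### Section 12 writes out its own lesion and progression rules beside the RECIST 1.1 named for eligibility, ORR and PFS, with no statement of which prevails and with a poor fit to this trial's imaging and eligibility

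*Combined protocol and SAP*

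**What the plan says.** RECIST 1.1 is named at each point that decides the result. Inclusion 6 in Section 4.0 reads "Have measurable disease based on RECIST 1.1". Section 2 sets the primary objective as "objective response rate (ORR) according to RECIST v1.1". Section 16.3 says "Tumor response (CR, PR, SD, or PD) will be defined according to RECIST v1.1 guideline", and 12.7 uses the same version for progression. The heading of 12.1 names it too.

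Section 12 then writes out rules of its own:

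- 12.2, measurability: "Each lesion must be ≥ 20 mm when measured by conventional techniques, including palpation, plain x-ray, CT, and MRI, or ≥ 10 mm" on spiral CT.
- 12.4, target lesions: "a maximum of 5 lesions per organ and 10 lesions in total", followed through the sum of longest dimensions. All disease must be followed with the technique used at baseline.
- 12.5, progression: a 20% rise in that sum from its smallest value; a separate 50% rule for a single pelvic mass measured by examination; and a global decline in health that forces a change of therapy, even with no objective finding.
- 12.6 is headed "Progression for Patients with Non-Measurable Disease at Baseline".

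On imaging, 10.1, 10.2 and the calendar in 10.8 schedule "MRI abdomen and pelvis with and without contrast". The only scheduled CT is of the chest.

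**The concern.** A reader who has to decide whether a lesion is measurable, which lesions enter the sum, or when a patient has progressed finds both a named guideline and a written rule. No passage ranks them, and none calls the written text a deliberate modification.

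Some of the written text also sits badly with this trial on the documents' own terms. The liver, the main metastatic site, is seen on MRI, and 12.2 puts MRI in the 20 mm group. Other parts address patients whom eligibility excludes, or conflict with the PFS definition in 16.3.

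At stake is whether eligibility, ORR, DCR, DOR and PFS are all measured on one scale. The primary decision has no slack: a single patient classified differently can change it.

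**Working it through.** **1. The rules side by side**

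| Question | Named source | Written rule | Fit with the rest of the plan |
|---|---|---|---|
| Which lesions are measurable? | RECIST 1.1 (inclusion 6) | 12.2: 20 mm on MRI, 10 mm only on spiral CT | Abdomen and pelvis by MRI only (10.1, 10.2, 10.8); spread mainly to the liver (1.7.3). That the liver is read on this MRI is an inference, but a plain one |
| Which lesions are targets? | RECIST 1.1 (2, 16.3) | 12.4: 5 per organ, 10 in total | No other passage gives a count; precedence is not stated |
| What is CR or PR of target lesions? | RECIST 1.1 (16.3) | None; 12.4 describes CR for non-target lesions only | Depends wholly on the reference in 16.3 |
| What is progression? | RECIST 1.1 (12.7); objective progression or death (16.3) | 12.5 also counts global decline with no objective finding | Direct conflict with 16.3 |
| Non-measurable disease at baseline? | Excluded by inclusion 6 | 12.6 gives a progression rule | Applies to no eligible patient |

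Because 12.4 holds each lesion to its baseline technique, a liver lesion first measured on MRI cannot later move to the 10 mm group.

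**2. What the measurability threshold can do to a patient** (lesion sizes are hypothetical)

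Two liver lesions on MRI measure 25 and 15 mm and grow to 28 and 22 mm.

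- Under 12.2 only the first is a target: 28/25 = 1.12, a 12% rise. This is below the 20% in 12.5, so there is no target-lesion progression.
- Under any rule that admits both: (28 + 22)/(25 + 15) = 50/40 = 1.25, a 25% rise. This is progression.

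Under the first reading the 15 mm lesion could still count if its growth were judged unequivocal non-target progression. The same dependence on the lesion set applies to shrinkage, but Section 12 gives no target-lesion PR threshold with which to show it.

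**3. What the progression conflict can do**

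Take a patient who declines globally, changes therapy and has no objective finding. Under 12.5 the PFS event falls on that date. Under 16.3 it does not: the event waits for objective progression or death, and if neither is seen, 12.7 censors the patient at the last progression-free assessment.

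**4. The design figures, and how close the decision is**

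Inputs (1.6 and 16.2): null ORR 5%, alternative 20%, stop at 0 of 13, reject at 4 or more of 27.

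P(reject | p) = sum over x = 1 to 13 of P(X1 = x; n = 13, p) × P(X2 ≥ 4 − x; n = 14, p)

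- p = 0.05: 0.0416 (stated 0.0416).
- p = 0.20: 0.8011 (stated 0.8011).
- Probability of stopping at stage 1: 0.95^13 = 0.513 under the null, 0.80^13 = 0.055 under the alternative.
- 3 of 27 = 11.1% (exact 95% CI 2.4 to 29.2%): not rejected.
- 4 of 27 = 14.8% (4.2 to 33.7%): rejected.

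The stated design reproduces, and reconciling the lesion rules changes neither N nor the boundaries. As an illustration with assumed shifts only, suppose the choice of rules lowered a true ORR of 20% to 18% or 17%: power would be 0.724 or 0.679. If it raised a true 5% to 6% or 7%, the rejection probability would be 0.072 or 0.111. The documents do not say that shifts of this size would occur.

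**The case against.** The strongest reply is that Section 12 opens under a RECIST 1.1 heading, so its rules may be meant as the guideline itself. The documents do not reproduce the guideline. A reader might infer that the 20 mm MRI threshold and the count of 5 and 10 contradict it, but the documents alone cannot show that. This stands. What remains is that two sources are given without precedence, and that the misfits with imaging, inclusion 6 and 16.3 are internal.

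A reader might also infer that Section 12 has no response rule at all. It does not go that far: 12.4 describes CR for non-target lesions, 16.3 defers the response categories to RECIST 1.1, and citing a guideline for them is legitimate. Nor is a contrast between lung and liver thresholds shown. The schedule calls the chest CT plain, never spiral, and 12.2 lists CT in the 20 mm group as well.

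It can fairly be said that 12.6 and the pelvic-mass rule look like leftover text with little or no effect. It is also true that nothing shows mixed use of the two sources in this single-site trial, and that sensitivity to one patient holds for any ORR question in this design. All of this limits the size of the point. It does not remove the conflict between 12.5 and 16.3, or the open question of which MRI threshold governs liver lesions.

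**Conclusion.** The point holds as one of consistency and precedence. Followed as written, the plan leaves open which rule decides measurability and target selection, and it gives conflicting answers on when progression without objective findings counts. The conclusion rests on the documents' own wording and on the inference that liver metastases are read on the abdominal MRI.

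Its size cannot be put as a number of patients. Lesion sizes are not given, so no loss at screening and no count of reclassified responders can be derived. What can be said is that one patient is enough to alter either decision: 0 versus 1 of 13 at stage 1, or 3 versus 4 of 27 at the end. A reader might infer a fault in the sample size; there is none, since both stated operating figures reproduce.

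**What to change.** State one criteria set for eligibility, ORR, DCR, DOR and PFS by referring to RECIST 1.1 for measurability, target selection, response and progression. Then:

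- Remove the parallel rules in 12.2, 12.5 and 12.6 and the target-lesion count in 12.4. Alternatively, keep them as a declared list of deviations, with a statement of precedence and a confirmed threshold for liver MRI.
- Reconcile 12.5 with 16.3 on progression without objective findings, and apply the answer to both PFS and DOR.
- Do not delete 12.4 wholesale. Keep the irradiated-lesion rule, the 4-week baseline limit and the same-technique rule as declared additions.
- Keep the survival definition in 16.3. If 12.6 goes, carry over its date of last contact, which the OS definition in 16.3 does not mention.

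The cost is protocol wording, with no additional scans or patients. The downside is that target-lesion lists of patients already enrolled need re-checking against the chosen rule.
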